## 6.1.2 Analysis of Primary Endpoint

The following process will be followed to analyze the primary endpoint using the MCP-MOD method.

## Step 1

A test statistic will be derived from the data using an analysis of covariance (ANCOVA) model with change from Baseline to Week 4 for the HAM-A Total Score as a response variable, treatment arm and Baseline value of HAM-A Total Score as covariates. Geographic region will be included as a covariate if clinical sites outside the US are used; otherwise, it will not be included in the model. Missing or potentially biased values occurring after IEs will be imputed as described in Section 6.1.1.

The ANCOVA model will be repeated for each imputed dataset, which results in a set of least squares (LS) mean estimates for all dose groups and the related covariance matrices. Rubin's rule will be used to combine the multiple sets of LS mean estimates and the related covariance matrices to a single set of LS mean estimates of change from Baseline to Week 4 for HAM-A Total Score for all dose groups and the related covariance matrix. The SAS procedure PROC MIANALYZE will be used to combine the results from imputed datasets and provide valid statistical inferences.

A range of possible dose-response relationships will be considered to take model uncertainty into account. The following six candidate dose-response curves, as depicted below in Figure 1, will be used to derive the optimal model contrasts for the multiple contrast tests:

- Sigmoid Emax (ED50, hill):
  - o 10, 1
  - o 100, 5
  - o 100, 10
  - o 150, 10
- Emax (D50 = 100)
- Linear

The optimal contrasts derived from the candidate model sets will be applied to the combined estimated dose means and covariance matrix to obtain the t-statistics for each candidate model and the common critical value  $C_{0.05}$  derived from the reference multivariate t-distribution with the 6x6 correlation matrix induced by testing the candidate dose-range models with respect to comparing all MM-120 doses to the placebo group.

The null hypothesis will be rejected and the statistical significance of dose-response in change from Baseline to Week 4 for HAM-A Total Score will be established if the max ( $t_1$ ,  $t_2$ ,  $t_3$ ,  $t_4$ ,  $t_5$ ,  $t_6$ )  $\ge C_{0.05}$ .

Mind Medicine, Inc. MMED008 Statistical Analysis Plan (Final version 1.0)

## Step 2

The response data in each imputed data set, including relevant covariates, will be used to fit the models in the candidate set. The estimated dose-response will be derived by using model averaging methods on a subset of candidate models, for which the associated contrast tests are statistically significant. The  $\leq$  3 models with the largest t-statistics  $\geq$  C0.05 as calculated above will be selected as the basis for the model averaging.

Dose

Model averaging will be carried out for each imputed dataset, and the resulting mean efficacy estimates, and CIs will be derived using the combination variance that accounts for the uncertainty of the imputed data using Rubin's combination rules. Comparisons between MM-120 doses and placebo will be simultaneously derived for the model averaged estimates together with the CIs reflecting the imputation procedure applied. The model-averaging-based estimates of the mean changes from Baseline to Week 4 for HAM-A Total Score within each dose group, and the mean

differences between MM-120 and placebo and their CIs will then be displayed.

Target dose selection (e.g., minimum effective dose [MED], EDp) will be based on the model change from Baseline to Week 4 for the HAM-A Total Score over the dose range studied. MED is defined as the lowest dose ensuring a clinically relevant and statistically significant improvement, MED = min{ $d \in (d_1, d_5) : f(d) > f(d_1) + \Delta$ }, where  $\Delta$  is the clinical relevance threshold. EDp is defined as the lowest dose that gives a certain percentage p of maximum effect  $\delta_{max}$ . EDp = min{ $d \in (d_1, d_5) : f(d) > f(d_1) + p\delta_{max}$ }. For this analysis, p will be set to 100%. The final choice of the target dose depends on the evaluation of the primary efficacy variable and other efficacy variables, as well as safety considerations.

The above will be repeated using only the model with the largest t-statistic  $\geq C_{0.05}$ .

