10.2.2. Efficacy Analyses

10.2.2.1. Primary Estimand

The primary estimand quantifies the treatment effect of MM-120 at 4 weeks post-dose administration while accounting for intercurrent events (IEs) with potential confounding effects and IEs leading to study discontinuation prior to the 4-week assessment.

The following attributes describe the primary estimand:

- Population: As defined by the Inclusion/Exclusion criteria
- Endpoint: Change from Baseline to Week 4 in HAM-A Total Score
- Treatment of interest /the randomized treatment: 4 doses of MM-120 (25, 50, 100, or 200 µg free-base equivalent) or placebo as a single-dose treatment.
- Handling of IEs prior to HAM-A assessment at Week 4:
 - Intake or change in concomitant medications/therapies which have potential confounding effects per the impact assessment.
 - Intake of prohibited medications/therapies assessed as "Yes" per the impact assessment.
 - *Policy strategy:* Available data recorded after the IE will be set to missing; such missing data will be imputed/substituted under a Missing Not at Random (MNAR) assumption by borrowing information from the placebo arm subjects (reference-based imputation).
 - IEs leading to study discontinuation due to other reasons.
 - IEs related to the COVID-19 pandemic
 Policy strategy: Available data will be used; missing data will be imputed under a Missing at Random (MAR) assumption, borrowing information from subjects in the same treatment arm.
- Summary measure: Identification of the dose-response curve and estimation of the target dose

Statistical Methods & Analysis

The MCP-Mod methodology (Bretz 2005; Pinheiro 2014) will be employed to assess the primary objective: to investigate the dose-response relationship for different doses of MM-120 versus placebo in change from Baseline in HAM-A Total Score at Week 4. An overview of the steps for the MCP-Mod methodology is given below.

Step 1

The analysis to derive the test statistics is based on an analysis of covariance (ANCOVA) model with the change from Baseline to Week 4 for HAM-A Total Score as a response variable, treatment (placebo and all MM-120 doses), and Baseline value of HAM-A Total Score. Centers will be pooled according to country and region as appropriate and as defined in the SAP prior to unblinding.

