## 4.7 Data Derivations and Transformations

The following derivations will be used in this study:

Study Day:

- Equal to (date of assessment date of first dose + 1) for assessments done on or after date of first dose
- Equal to (date of assessment date of first dose) for assessments before date of first dose

Baseline Observation: the last non-missing value prior to first study drug administration.

Duration: end date – start date +1; measured in days.

Change from Baseline: post-baseline value - baseline value

Percent Change from Baseline: (post-baseline value - baseline value) / baseline value x 100

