## 6.1 Primary Efficacy Endpoint and Analysis

The primary efficacy endpoint is change from Baseline to Week 4 in HAM-A Total Score. The MCP-MOD method (Bretz 2005; Pinheiro 2014) will be used to assess the primary endpoint to investigate the dose-response relationship for the 4 doses levels of MM-120 versus placebo. The analysis of the primary endpoint using MCP-MOD will be performed on the FAS population. A sensitivity analysis will be performed on the PPS population.

The HAM-A consists of 14 items that encompass both psychological and somatic symptoms of anxiety. The HAM-A takes about 20 minutes to administer and will be completed by a central rater. The central rater will assess the extent to which the subject displays each given criterion and give a rating on a scale of 0-4, where 4 represents the most severe symptoms. The HAM-A Total Score will be calculated as the sum of the 14 items and will range from 0-56. Higher Total Scores

indicate increased severity of symptoms.

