## 9 SAMPLE SIZE AND POWER CALCULATIONS

A total sample of 180 subjects, 36 per arm, is required to ensure a mean power >87% for an MCP-Mod Analysis rejecting the hypothesis of a constant dose-response curve using the multiple comparisons procedure (MCP), assuming a null placebo response, a maximum standardized effect of 0.6 within the doses range, and a common standard deviation within the dose arms, if a studywise one-sided type-1 error rate <0.05 is required.

The analysis assumes 4 doses of active medication (25, 50, 100 and 200  $\mu$ g freebase-equivalent) and placebo. The required sample size for each arm is 36 subjects.

The R package Dose Finding (https://CRAN.R-project.org/package=DoseFinding) has been used to estimate the sample size and corresponding power. The power for each model is estimated as shown Table 6.

Table 6	Power by Mode

Model	Power (%)
Sigmoid Emax (ED50, hill)	
10, 1	84.5
100, 5	90.7
100, 10	91.0
150, 10	89.9
Emax (D50 = 100)	83.2
Linear	85.0

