## 1 INTRODUCTION

This statistical analysis plan (SAP) addendum describes the planned statistical analysis to be performed for the study, MMED008 entitled "A Phase 2, Multi-center, Randomized, Double-Blind, Parallel-Group, Dose-Finding Study to Assess the Effect of Four Doses of MM-120 for the Treatment of Anxiety Symptoms." has been engaged by Mind Medicine, Inc. (the 'sponsor') to develop the SAP and carry out the statistical analysis described in this SAP Addendum, including production of all tables, figures and listings.

This SAP addendum details statistical analyses that were added to the study after the unblinded review of the Primary Efficacy Endpoint. Thus, these analyses were not pre-planned in the protocol or SAP and are considered ad-hoc. This addendum contains no changes to the original pre-planned analyses contained in the final SAP, version 1.0 dated 01Aug2023.

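### The SAP's MED and EDp formulas point toward worsening on the HAM-A change scale, Δ has no value, and EDp at p = 100% has no solution even with the sign corrected

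*SAP*

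**What the plan says.** Protocol 10.2.2.1 gives the summary measure of the primary estimand as "Identification of the dose-response curve and estimation of the target dose". It leaves the algorithm to the SAP.

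SAP 6.1.2, Step 2, says that target dose selection "will be based on the model change from Baseline to Week 4 for the HAM-A Total Score over the dose range studied", with MED and EDp as its two examples. In words, "MED is defined as the lowest dose ensuring a clinically relevant and statistically significant improvement". In symbols:

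- MED = min{d in (d1, d5) : f(d) > f(d1) + Δ}, where Δ is called the clinical relevance threshold and is given no number.
- EDp = min{d in (d1, d5) : f(d) > f(d1) + p·δmax}. The SAP then adds "For this analysis, p will be set to 100" per cent.

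Two other sections fix the scale. SAP 4.7 has "Change from Baseline: post-baseline value - baseline value". SAP 6.1 scores each HAM-A item from 0 to 4, "where 4 represents the most severe symptoms", and higher totals mean greater severity. Step 1 of 6.1.2 uses that change as the response, with no sign reversal stated.

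The SAP Addendum (Section 1), written after the unblinded review of the primary endpoint, states: "This addendum contains no changes to the original pre-planned analyses contained in the final SAP".

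**The concern.** A drug that works lowers f, so a rule asking for f(d) above f(d1) plus a threshold looks for a dose worse than placebo. The sentence around the formula asks for the opposite.

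Three further gaps are separate from the sign:

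- The verbal MED requires statistical significance, but the formula has no such condition, and no confidence level is given for the Step 2 intervals.
- Δ is undefined. The 0.6 in SAP 9 is a power assumption in SD units, and no SD in HAM-A points is given from which to convert it.
- EDp at 100% with a strict inequality asks for a dose that exceeds the maximum effect.

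MED and EDp are the only target-dose quantities the SAP defines. The same text governs the Week 8 key secondary analysis (SAP 6.2.1) and the repeat with the single best model. A Δ chosen after unblinding could be chosen knowing the curve.

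**Working it through.** **Inputs.** From SAP 6.1.2 and 9: six candidate curves, doses 0, 25, 50, 100 and 200 µg, 36 per arm, one-sided 0.05, and "a maximum standardized effect of 0.6 within the doses range". Assumed: |Δ| = 0.2, 0.3, 0.4 and 0.5 SD, giving 6 × 4 = 24 cases; and d5 = 200 µg, counting placebo as d1.

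**1. The plan's own figure.** Optimal contrasts with 175 df and a simulated max-t test (2,000,000 draws) give a critical value of 2.04 and the powers in the table. Their mean is 87.5%. The stated values average (84.5 + 90.7 + 91.0 + 89.9 + 83.2 + 85.0)/6 = 87.4%. The power claim reproduces.

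**2. MED as printed.** Write g(d) = f(d) − f(d1) = −0.6 × m(d)/m(200) SD, where m(d) = d^h/(ED50^h + d^h), or m(d) = d for the linear curve. The printed rule is g(d) > Δ.

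- Δ > 0: g is negative at every dose above zero, so no dose qualifies in 24 of 24 cases.
- Δ < 0, continuous search: every dose with an effect smaller than |Δ| qualifies, starting just above zero. The result is about 0 in 24 of 24.
- Δ < 0, tested doses 25, 50 and 100 µg (the printed open interval excludes 200): the 25 µg effect is 0.6 × (25/35)/(200/210) = 0.45 SD for sigmoid (10, 1), 0.6 × (25/125)/(200/300) = 0.18 SD for Emax, 0.6 × 25/200 = 0.075 SD for linear, and below 0.001 SD for the other three. The rule returns 25 µg in 21 cases. It returns nothing in the other 3, which are sigmoid (10, 1) at |Δ| = 0.2, 0.3 and 0.4.

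**3. MED with the direction corrected.** Use g(d) ≤ −Δ on (0, 200], point estimate only, on a 0.1 µg grid. The table gives Δ = 0.3 SD. The answer depends heavily on Δ: for the linear curve it runs from 200 × 0.2/0.6 = 66.7 µg to 200 × 0.5/0.6 = 166.7 µg.

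**4. EDp on an improvement scale.** Let h(d) = −g(d), whose maximum in range is 0.6 at 200 µg. At p = 100%:

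- h(d) > 0.6 has no solution for any curve.
- h(d) ≥ 0.6 on the open interval has none either.
- h(d) ≥ 0.6 with 200 included gives 200 µg for all six, whatever the shape.

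If δmax means the model asymptote, it is 1/m(200) times the 200 µg effect. That ratio exceeds 1 for all five Emax-type curves, so no dose in range qualifies for them.

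| Curve | Power stated / recomputed (%) | Corrected MED, Δ = 0.3 SD (µg) | EDp, p = 100%, strict | EDp, p = 90%, ≥ (µg, illustrative) | Asymptote ÷ 200 µg effect |
|---|---|---|---|---|---|
| Sigmoid (10, 1) | 84.5 / 84.6 | 9.1 | none | 60.0 | 1.050 |
| Sigmoid (100, 5) | 90.7 / 90.7 | 98.8 | none | 147.0 | 1.031 |
| Sigmoid (100, 10) | 91.0 / 91.0 | 100.0 | none | 124.5 | 1.001 |
| Sigmoid (150, 10) | 89.9 / 90.0 | 148.5 | none | 178.7 | 1.056 |
| Emax (100) | 83.2 / 83.3 | 50.0 | none | 150.0 | 1.500 |
| Linear | 85.0 / 85.1 | 100.0 | none | 180.0 | no asymptote |

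These are outputs of the formulas, not dose recommendations.

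**5. Why the confidence level matters.** With 36 per arm the unadjusted pairwise SE is √(2/36) = 0.236 SD. On 174 df the margin is 0.390 SD at one-sided 95% and 0.465 SD at two-sided 95%. Model-averaged margins will differ, but a significance condition clearly depends on the level.

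**The case against.** The strongest reply is that the direction is a slip of notation. The MED sentence says improvement. Step 1 also needs an unstated orientation, because it rejects for large positive t while modelling the same change score, and SAP 9 speaks of a positive maximum effect. If f is read as a reduction, the MED formula works. The candidate-curve figure could not be consulted here and may show that orientation. An empty result would also be noticed at programming, so it is unlikely to bias anything silently. The intent is indeed clear, but no text in either document states the convention, and a correct reading still leaves Δ and the confidence level open.

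On EDp, the argument rests on a strict sign and a round bracket, which should be checked against the signed SAP. The verbal definition (the lowest dose giving a percentage p of the maximum effect) is non-strict. At 100% it does have an answer if δmax is the in-range maximum and d5 is included. That answer is the top of the range for every increasing curve, so it is uninformative rather than undefined. This softens the finding without removing it.

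Finally, MED and EDp are given as examples, the final choice also weighs other efficacy variables and safety, and only models with a significant contrast reach Step 2. All true. The last is an overall gate, though, not the dose-specific significance that the MED wording requires. Missing Δ and an unstated interval level alone would be ordinary gaps in detail; the sign and the p = 100% rule are wrong as written.

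**Conclusion.** The concern holds. On the scale the SAP defines, neither sign of Δ makes the printed MED usable: no dose in 24 of 24 cases, or about zero in 24 of 24 on a continuous search. EDp at 100% has no solution as printed on an improvement scale. Its least restrictive repair returns 200 µg for all six curves.

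The counts assume monotone improvement with the maximum at 200 µg and the illustrative |Δ| values. The exclusion of the top dose assumes that d5 is 200 µg and that the bracket is as printed.

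The scope is limited. Stated power reproduces, and the max-t test and type I error are not shown to be affected, provided the Step 1 contrasts are oriented so that benefit gives positive t. What needs correcting is the target-dose part of the primary estimand's summary. These documents contain no Δ fixed before unblinding.

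**What to change.** 1. **Direction.** Either define f as baseline minus post-baseline, or write MED = min{d in (d1, d5] : f(d) ≤ f(d1) − Δ and the upper confidence limit of f(d) − f(d1) is below 0}, with Δ > 0. State the same orientation for the Step 1 contrasts, and say that the interval now includes d5.
2. **Confidence level.** State it. One-sided 95% would match the plan's one-sided 0.05; the two-sided 95% used for the secondary endpoints is the alternative.
3. **EDp.** Reorient it in the same way, use a stated p below 100%, and say whether δmax is the in-range maximum or the asymptote. If p stays at 100%, use ≥ with d5 included and say that it returns the top dose for any strictly monotone fit.
4. **Δ.** Cite a dated value in HAM-A points set before unblinding. If none exists, report the MED as post hoc over a range of Δ.

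The cost is SAP wording and a few stated values; no new data are needed. The sponsor must commit to a Δ. If it was not set before unblinding, the report carries a range of MEDs instead of one value.

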## 6.2 Key Secondary Efficacy Endpoint and Analysis

## 6.2.1 Key Secondary Endpoint

The key secondary endpoint is change from Baseline to Week 8 in HAM-A Total Score. Analysis of this endpoint will follow the same process as the primary endpoint described in Section 6.1. The outcome for this endpoint will be considered confirmatory, if in agreement with the primary endpoint outcome and provided that the null hypothesis is rejected for the primary outcome. This gatekeeping function of the primary outcome allows for no adjustment of alpha level for multiplicity of testing.

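### EDp with p = 100% returns the top studied dose for any rising fit, so this target-dose metric says nothing about curve shape

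*SAP*

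**What the plan says.** The primary estimand in Protocol 10.2.2.1 ends with "Summary measure: Identification of the dose-response curve and estimation of the target dose". The protocol gives no value of p and leaves the algorithms to the SAP.

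SAP 6.1.2 supplies the rule:

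- **Candidate set (Step 1).** "The following six candidate dose-response curves, as depicted below in Figure 1" are sigmoid Emax with (ED50, hill) of (10, 1), (100, 5), (100, 10) and (150, 10), Emax with ED50 of 100, and linear. None is umbrella-shaped.
- **Estimated curve (Step 2).** Up to three models with significant contrasts are averaged. Then "The above will be repeated using only the model with the largest t-statistic" at or above the critical value.
- **Target-dose metrics (Step 2).** MED and EDp are given as examples, both taken over the studied range. EDp is "the lowest dose that gives a certain percentage p of maximum effect", and "For this analysis, p will be set to 100" per cent. The printed formula uses a strict inequality on the open interval (d1, d5).
- **Limit on their role (Step 2).** "The final choice of the target dose depends on the evaluation of the primary efficacy variable and other efficacy variables", together with safety.

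For Week 8, SAP 6.2.1 says "Analysis of this endpoint will follow the same process as the primary endpoint described in Section 6.1".

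**The concern.** A target-dose metric in a dose-finding trial should give different answers for different curve shapes. With p at 100% and only monotone models, the answer is the top of the range before any data are seen, provided the fits rise with dose. Models enter Step 2 by passing a one-sided test for improvement, so rising fits are the expected case.

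Three things follow. A reported value of 200 µg could be misread as evidence that the effect is still growing at the top dose. Repeating the analysis with the single best model gives the same value, so that repeat cannot show model sensitivity in this metric. And the other named metric, MED, has no numerical threshold in the documents. As written, then, neither named metric can give an informative target dose.

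**Working it through.** **Inputs.** Doses 0, 25, 50, 100 and 200 µg, 36 per arm, maximum standardized effect 0.6, one-sided 0.05 (SAP 9); the six candidate curves (SAP 6.1.2 Step 1); p = 100% (Step 2).

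**1. Reproduce the SAP's power.** Equal-n optimal contrasts, multivariate t with 180 − 5 = 175 df, 2,000,000 draws, critical value 2.04.

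| Model | SAP Table 6 (%) | Recomputed (%) |
|---|---|---|
| Sigmoid (10, 1) | 84.5 | 84.6 |
| Sigmoid (100, 5) | 90.7 | 90.7 |
| Sigmoid (100, 10) | 91.0 | 91.0 |
| Sigmoid (150, 10) | 89.9 | 90.0 |
| Emax (100) | 83.2 | 83.3 |
| Linear | 85.0 | 85.1 |
| Mean | 87.4 | 87.4 |

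The planning set-up is therefore the one the SAP used.

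**2. EDp in closed form.** For a sigmoid Emax curve write f(d) = d^h / (d^h + ED50^h), and F = f(200). Taking the maximum effect as the in-range maximum,

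EDp = ED50 × [pF / (1 − pF)]^(1/h).

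At p = 1, F / (1 − F) = (200 / ED50)^h, so EDp = ED50 × (200 / ED50) = 200 whatever ED50 and h are. Emax is the case h = 1. For the linear curve EDp = 200p, which is also 200 at p = 1. A positively weighted average of rising curves rises too, so its in-range maximum is again at 200.

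Below 100% the metric separates the shapes. Example for (10, 1): F = 200/210 = 0.952; at p = 0.8, pF = 0.762 and ED80 = 10 × 0.762/0.238 = 32.0 µg.

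| Model | ED50 | ED80 | ED90 | ED100 | Share of 200 µg effect reached at 100 µg |
|---|---|---|---|---|---|
| Sigmoid (10, 1) | 9.1 | 32.0 | 60.0 | 200 | 95.5% |
| Sigmoid (100, 5) | 98.8 | 128.2 | 147.0 | 200 | 51.6% |
| Sigmoid (100, 10) | 100.0 | 114.8 | 124.5 | 200 | 50.0% |
| Sigmoid (150, 10) | 148.4 | 168.1 | 178.7 | 200 | 1.8% |
| Emax (100) | 50.0 | 114.3 | 150.0 | 200 | 75.0% |
| Linear | 100.0 | 160.0 | 180.0 | 200 | 50.0% |

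**3. Other readings.** The printed strict inequality on the open interval admits no dose at p = 100%. If the maximum effect means the fitted asymptote, the planning Emax and sigmoid Emax curves reach only 66.7% to 99.9% of it at 200 µg, so no studied dose qualifies. On these readings the metric is undefined or unattainable; it is not informative on any of them.

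**4. Behaviour after refitting.** 5,000 trials for each of the six true curves (30,000 in all), critical value 2.044. In each significant trial the three or fewer models with the largest qualifying t were refitted by least squares and averaged, and EDp was solved. Assumptions not in the documents: AIC weights, ED50 bounded to 0.2–300 µg, hill to 0.5–10, no covariate, no missing data.

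- 26,218 trials were significant. In 26,217 every selected fit rose with dose and ED100 was 200 µg. In the other one the only selected fit fell with dose.
- In 409 of these (409 / 26,217 = 1.6%) the curve equals f(200) to machine precision below 200 µg, so software could print a lower dose through rounding alone.
- Median ED80 (10th to 90th percentile): 34 (1–136) µg under (10, 1); 150 (96–174) µg under linear; 176 (137–196) µg under (150, 10).
- Chance that a trial from (10, 1) gives a lower value than one from linear: 0.91 for ED80, against 0.50 (all ties) for ED100.
- Averaged and single-best ED80 differ by at least 25 µg in 5% to 32% of significant trials, depending on the true curve. ED100 never differs when the selected fits rise.

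**The case against.** The strongest case against is about consequence. EDp is introduced only as an example, beside MED, and the final choice draws on other efficacy variables and safety. Model-averaged means and differences from placebo with intervals are displayed for each dose, and ANCOVA comparisons by visit are planned (SAP 6.3.1), so the shape remains visible. The single-model repeat also covers those estimates, where model sensitivity can show. All of this stands and limits the point to one metric.

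Second, returning 200 µg depends on a reading: the SAP does not say whether the maximum effect is in-range or asymptotic. That is correct, but the alternatives leave no qualifying dose for the Emax-type fits, so they do not rescue the rule.

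Third, some simulation figures depend on averaging weights the SAP does not give. With equal weights, median ED80 under (10, 1) is 71 µg instead of 34, and the 5% to 32% range becomes roughly 2% to 45%. Four candidates share one functional form once refitted; in a smaller rerun, merging such duplicates moved the figure for (100, 5) from 24% to 33%. Those two illustrations are therefore soft. The 0.91 separation holds under equal weights, and the constancy of ED100 needs no weights at all.

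Fourth, Step 2 ties target-dose selection to Week 4, and SAP 6.2.1 names no Week 8 target dose. Its instruction to follow the same process still carries the rule over.

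**Conclusion.** The concern holds. As specified, EDp equals the highest studied dose for every rising fit from the candidate set, at Week 4 and, through SAP 6.2.1, at Week 8. This follows from algebra under the in-range, at-least reading; the other readings yield no usable value for the Emax-type fits. The size of the loss is clearest in the planning curves: the share of the 200 µg effect already reached at 100 µg runs from 1.8% to 95.5%, yet all give the same EDp.

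The simulated ED80 figures rest on the stated weights, bounds and complete data. They show what the metric discards and do not recommend a dose. The MCP test, type I error, power and dose-level estimates are unaffected. It should be fixed because target-dose estimation is part of the primary estimand's summary measure and the instruction on p is firm.

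**What to change.** In SAP 6.1.2 Step 2:

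- Specify one or more p values below 100% (50%, 80% or 90%, for example; the choice is the sponsor's).
- Define the maximum effect as the modelled maximum within the studied range.
- Write the condition as at least, on the closed interval [d1, d5], and say plainly that larger f means more improvement, since improvement on HAM-A is a negative change.
- Report each EDp with an interval that reflects model averaging and imputation, at Week 4 and Week 8.

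This takes a few lines of text and code, needs no new data, and leaves the MCP test and power alone. There are two costs. EDp will carry visible uncertainty, which can be wide: under (10, 1) the simulated 10th to 90th percentile of ED80 was 1 to 136 µg. And the SAP Addendum's Introduction records that the primary endpoint has been reviewed unblinded, so new EDp values cannot be called pre-specified. They should be labelled ad hoc, as the Addendum labels its own additions.
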